10 SAFETY ANALYSES

10.1 Overview of Safety Analysis Methods

All safety analyses will be performed using all participants in the safety population, regardless of eligibility. The frequency of toxicities potentially attributable to pomalidomide treatment will be determined (e.g., venous/arterial thromboembolism, thrombocytopenia, fatigue, constipation/diarrhea, rash). Treatment and resolution of all safety endpoints will also be documented. Treatment groups will be compared for incidence of events with a chi-squared or Fisher's exact test, and incidence density (events per person-months of exposure) will be calculated for toxicities in the pomalidomide group. Adverse event incidence rates will be included in semi-annual safety reports to the DSMB and annually to the FDA.

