## 8.5 STUDY HALTING RULES

Randomization of new participants will be halted when eight thromboembolic events, defined as any venous thromboembolic event requiring medical intervention (grade 2 or higher) or any arterial thromboembolic event, that are determined to be related or "probably related" to the study drug are reported to the DCC.

The DCC will notify the study monitor, study sponsor, PI and investigators immediately when the eighth thromboembolic event (as defined above) is reported and randomization functionality will be deactivated. The PI will inform the DSMB members within 24 hours of this occurrence and the DCC will provide the DSMB with AE listing reports. The DSMB will convene an ad hoc meeting by teleconference or in writing as soon as possible. The DSMB will provide recommendations for proceeding with the study to the study sponsor/NIH. The clinical coordinating center will inform NHLBI and the FDA of the temporary enrollment halt and the disposition of the study.

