## 10.4 DESCRIPTION OF STATISTICAL METHODS

### 10.4.1 GENERAL APPROACH

This is a Phase II trial in which the primary goal is to evaluate the safety and efficacy of pomalidomide in the treatment of epistaxis in patients with HHT.

For descriptive statistics, categorical data will be presented as proportions and 95% confidence intervals and continuous data as means with standard deviations, median, and range. Estimates from linear models will be presented by mean, standard error, and 95% CI. Estimates from logistic regression will be presented by odds ratios and 95% CIs. All statistical tests will be 2-tailed.

Checks of assumptions (e.g., normality) underlying statistical procedures will be performed and corrective procedures such as use of a transformation or application of nonparametric tests will be applied.

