7 STATISTICAL/ANALYTICAL ISSUES

7.1 General Rules

All statistical computations will be performed, and data summaries created using SAS 9.4 or higher. For summaries of study data, categorical measures will be summarized in tables listing the frequency and the percentage of subjects in each study arm; continuous data will be summarized by presenting mean, standard deviation, median and range; and ordinal data will be summarized by presenting median and range.

Estimates from linear models will be presented by mean, standard error, and 95% CI. Estimates from logistic regression will be presented by odds ratios and 95% CIs. All statistical tests will be 2-tailed.

Checks of assumptions (e.g., normality) underlying statistical procedures will be performed and corrective procedures such as use of a transformation or application of nonparametric tests will be applied.

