7.4 Interim Analyses and Data Monitoring

Safety outcomes will be assessed at each DSMB meeting. Rates of safety outcomes will be compared between treatment groups using Fisher's exact tests and provided to the DSMB. At each meeting, the DSMB will be presented with information about enrollment and outcome data attainment (for

example, the percent of expected visits that have been completed) to allow them to determine that the study is making reasonable progress. These review meeting will occur once each 6 months.

A formal interim analysis for efficacy after 50% and 75% of patients have completed the 24-week treatment period or discontinued from the study. See Section 9.6 for details.

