7.7 Multiple Comparisons and Multiplicity

For inferential tests, the p-value for determination of statistical significance (Type I error) for the single primary efficacy outcome (change in ESS from baseline to week 24) will be evaluated relative to 0.044 to adjust for the interim efficacy analysis (see Section 9.6). However, the 75% interim analysis was conducted at 80% due to timing of DSMB meetings. This changed the significance level for the primary outcome from 0.044 to **0.0425** (see Appendix 3).

Significance of the treatment group comparison for 5 key secondary outcomes will be evaluated as follows: If the primary endpoint is found statistically significant at $p < 0.0425$, then the key secondary endpoints will be evaluated for statistical significance with a Hochberg modification to the Bonferroni adjustment (Hochberg, 1988), in which the p-values of the 5 outcomes will be ordered. The largest p-value will be compared relative to $p < 0.05$, and if met, all 5 endpoints will be considered significant. If not, then the second largest p-value will be assessed relative to $p < 0.05/2 = 0.025$, and if met then it and the other three endpoints will be considered significant, and so on for the third p-value compared at $0.05/3 = 0.017$, the fourth compared to $0.05/4 = 0.012$, and the fifth compared to $0.05/5 = 0.010$. Results from analyses of all other secondary endpoints and subgroup analyses will not be evaluated relative to statistical significance.

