12 CHANGES TO THE ANALYSES PLANNED IN THE PROTOCOL

The SAP expands the analysis of the primary and second endpoints described in the protocol. No changes from that specified in the protocol were made.

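### Safety has no planned between-arm estimate with uncertainty, and the SAP leaves out the per-arm 95% confidence intervals that the protocol specifies

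*SAP*

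**What the plan says.** Determining safety and tolerability is the first secondary objective (Protocol 3.2, SAP 3.1.2). Incidence and severity of adverse events is item 7 of the other secondary outcomes in SAP 3.2.3.

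- **Final analysis, SAP 10.1:** "Treatment groups will be compared for incidence of events with a chi-squared or" Fisher's exact test. Protocol 10.4.4 has the same sentence. Incidence density is planned for the pomalidomide arm only.
- **Abnormal laboratory values, SAP 10.4:** the same two tests, if applicable.
- **DSMB reports, SAP 7.4:** "Rates of safety outcomes will be compared between treatment groups using" Fisher's exact tests.
- **Event tables, SAP 10.2 and 10.3:** numbers of events and of affected participants by arm, severity and relatedness, with listings of SAEs and deaths. No interval is mentioned.
- **General rule, Protocol 10.4.1:** "categorical data will be presented as proportions and 95% confidence intervals".
- **General rule, SAP 7.1:** "categorical measures will be summarized in tables listing the frequency and the percentage of subjects in each study arm".
- **Departures, SAP 12:** "No changes from that specified in the protocol were made".
- **Role of the p-values, SAP 7.7:** "Results from analyses of all other secondary endpoints and subgroup analyses will not be evaluated relative to statistical significance".

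**The concern.** Two gaps combine. First, the SAP's general rule no longer includes the per-arm 95% interval in the protocol's general rule, and the section meant to record departures says there are none. Second, the only between-arm safety method named is a test that returns a p-value. That p-value has no decision role under SAP 7.7, and nothing in the plan gives the size of an excess with its uncertainty.

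A safety objective in a trial of this size is mainly a question of what excess the data can exclude. A p-value does not answer that, least of all for rare events such as thromboembolism. If the plan is followed to the letter, the tables will show counts and p-values, and readers will have to work out the bounds themselves. Neither document states what excess of any toxicity the trial could detect or rule out. The only binary difference given a power is 30 points, for the transfusion or iron endpoint (SAP 6).

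**Working it through.** **Inputs**

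- Planned size 159, split 106:53 (SAP 6). The site counts in SAP 7.6 sum to 24 + 51 + 21 + 16 + 12 + 21 = 145; a 97:48 split is assumed for a second run.
- Tests are two-tailed (SAP 7.1). No alpha is given for safety; 0.05 is assumed, as in Protocol Table 9.
- Toxicity rates in HHT are not given, and Protocol 2.3.1 calls them unknown. All rates below are assumptions, shown as a range.

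**Step 1. Reproduce the plan's own binary power (Protocol Table 9).**

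Power = Φ{[d - 1.96·√(p̄(1-p̄)(1/n1+1/n2))] / √(p1(1-p1)/n1 + p2(1-p2)/n2)}

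For 60% vs 90% at 96:48:

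- p̄ = (57.6 + 43.2)/144 = 0.70
- Null SE = √(0.21 × 0.03125) = 0.0810
- Alternative SE = √(0.0025 + 0.001875) = 0.0661
- (0.30 - 0.1588)/0.0661 = 2.14, so power is 98.4% (stated 98%)

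The other five entries come out at 95.6, 96.7, 92.9, 94.3 and 89.7%, against 96, 97, 93, 94 and 90% stated. All agree.

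**Step 2. Exact power for harms.**

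Power = Σa Σb Bin(a; n1, p1)·Bin(b; n2, p2)·1{p-value ≤ 0.05}, summed over every 2×2 table.

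| Pomalidomide vs placebo | Fisher, 106:53 | Uncorrected chi-squared, 106:53 | Fisher, 97:48 |
|---|---|---|---|
| 5% vs 1% | 5% | 10% | 3% |
| 7.5% vs 0%* | 40% | 55% | 31% |
| 7.5% vs 1%* | 25% | 36% | 20% |
| 10% vs 5% | 12% | 16% | 10% |
| 15% vs 5% | 41% | 48% | 37% |
| 20% vs 10% | 31% | 35% | 29% |
| 30% vs 20% | 23% | 26% | 21% |
| 25% vs 10% | 60% | 63% | 55% |
| 20% vs 5% | 73% | 78% | 69% |
| 40% vs 20% | 71% | 74% | 67% |
| 30% vs 10% | 83% | 85% | 78% |

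*The chi-squared and 97:48 entries in these rows were run at 8/106 = 7.55%, where Fisher at 106:53 gives 41% and 26%.

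One case with an excess under 10 points passes one half: 10% vs 1% has Fisher power 52% at 106:53.

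**Step 3. What an interval adds.** Take eight events on pomalidomide and none on placebo, one per participant, at 106:53.

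- Fisher p = 0.053.
- Uncorrected chi-squared = 159 × (8 × 53)² / (106 × 53 × 8 × 151) = 4.21, p = 0.040.
- SAP 10.1 allows either test and gives no rule for choosing. The expected placebo count is 8 × 53/159 = 2.7, so Fisher would be the usual choice.
- Risk difference = 8/106 = 7.5 points. Wilson limits are 3.9% to 14.2% for 8/106, and 0 to 6.8% for 0/53.
- Newcombe lower limit: 7.55 - √((7.55 - 3.87)² + 6.76²) = -0.1. Upper limit: 7.55 + (14.19 - 7.55) = 14.2.

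Other tables at 106:53, with Newcombe 95% limits:

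| Events | Fisher p | Risk difference, points (95% CI) |
|---|---|---|
| 5 vs 0 | 0.17 | 4.7 (-2.6 to 10.6) |
| 10 vs 3 | 0.55 | 3.8 (-6.8 to 11.8) |
| 21 vs 5 | 0.11 | 10.4 (-2.2 to 20.5) |

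**Step 4. Zero counts.** The masked review in SAP 9.2 found no arterial thromboembolism terms. For 0/106 the exact two-sided 95% upper limit is 1 - 0.025^(1/106) = 3.4%; for 0/97 it is 1 - 0.025^(1/97) = 3.7%. The planned summaries do not call for this figure.

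**The case against.** A reader might infer stronger forms of this point. The case against them is good.

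- **That the plan treats p > 0.05 as safe.** No text says so, and SAP 7.7 points the other way. This objection stands.
- **That monitoring depends on these tests.** It does not. Protocol 8.5 says "Randomization of new participants will be halted when eight thromboembolic events", counted by type and relatedness and without reference to any p-value. The medical monitor reviews all adverse events, and the DSMB receives summaries of AEs and SAEs. The 8 vs 0 table therefore shows what an interval adds; it does not show a failed safeguard. This stands.
- **That the SAP removed a planned between-arm interval.** It did not. The intervals in Protocol 10.4.1 are per-arm and descriptive, and Protocol 10.4.4 never planned a risk difference. The missing contrast comes from the protocol; the missing per-arm interval is new in the SAP. This stands.
- **That the tests miss relevant harm most of the time.** This is too broad. Power is 60% or more in the 15-point and 20-point scenarios above at 106:53, and the documents define no relevant excess.
- **That the information is absent.** Counts by arm, severity and relatedness are reported, so a reader can derive a difference and its interval. This stands in part, because the plan does not commit to reporting either.

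Two defences are weaker. SAP 9.4 assigns other yes/no outcomes to logistic regression, and SAP 7.1 attaches 95% intervals to odds ratios. That text is in the efficacy section, however, and SAP 10.1 names its own method for safety. The table shells are in a separate document (SAP 14) and may include intervals, but the SAP text does not require them.

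**Conclusion.** The point holds as a gap in estimation. SAP 7.1 omits an interval that Protocol 10.4.1 states, and SAP 12 does not declare it. For the safety objective, no between-arm estimate with uncertainty is planned.

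The gap matters most for uncommon events. At 106:53, Fisher power is 5% for 5% vs 1%, 25% for 7.5% vs 1%, and 31% to 41% for the 10-point excesses over placebo rates of 10% and 5%. For larger excesses the test is more useful: 60% for 25% vs 10% and 73% for 20% vs 5%. In the four tables with events in Step 3, a Fisher p-value above 0.05 goes with an upper limit of about 11 to 21 excess cases per 100.

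These figures rest on assumed event rates, two-sided alpha 0.05, one event per participant and the planned 106:53 split. Power is lower throughout the table at 97:48. The documents do not support reading this as a wrong decision rule or a biased result. Neither the primary analysis nor the thromboembolism halt is affected.

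**What to change.** 1. In SAP 7.1 and 10.1, give each arm's incidence with an exact (Clopper-Pearson) 95% interval, including when the count is zero. Otherwise, declare the departure from Protocol 10.4.1 in SAP 12.
2. In SAP 10.1 and the DSMB tables under SAP 7.4, add the risk difference with a two-sided 95% interval for each protocol-named toxicity and for SAEs. Use a method suited to small counts, such as Miettinen-Nurminen or Newcombe.
3. Keep the chi-squared or Fisher p-values, labelled as descriptive, in line with SAP 7.7.

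The cost is SAP wording and a few table columns from data already collected. Conduct and sample size do not change. Intervals do not cure low power: many will be wide, and the safety statement will look less favourable than a bare p-value above 0.05.

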#### 6.1.9 DURATION OF THERAPY

The duration of pomalidomide therapy will be 24 weeks.

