### 10.5 SAMPLE SIZE

We will randomize 159 patients, 106 on pomalidomide, 53 on placebo.

**Design:** Since HHT is a rare disorder and our study is unlikely to be repeated, we wish to power the study at 90%. To assist in participant recruitment, we will randomize in a 2:1 ratio of pomalidomide to placebo in order to maximize active intervention for study participants and also maximize the amount of safety data for pomalidomide. Treatment group comparison for the single primary endpoint will be evaluated for statistical significance relative to alpha <0.0444, reduced from 0.05 to adjust for two planned interim analyses after 50% and 75% of patients complete the treatment period (see section 10.4.7.2).

**Effect Size:** The primary endpoint is ESS change from baseline to 24 weeks. We wish to power the study to identify a difference between pomalidomide and placebo of 1.0. Table 6 provides a summary of ESS scores from available HHT studies. In our small pilot study of patients with moderate to severe epistaxis treated with pomalidomide, we found an average reduction in ESS score at 24 weeks of 2.7. On the other hand, the NOSE study of 121 HHT patients identified an improvement in ESS across all study participants receiving placebo or non-effective treatments of 1.5 at 12 weeks. Although we anticipate a difference of at least 1.2 between groups in our study, we have planned the sample size to detect a difference of 1.0. This value is above the estimated minimally important difference of 0.7 as determined by patient's assessment of QOL. We conservatively estimate that the standard deviation for the ESS change from baseline score will be 1.7, based on standard deviations from the

recent large double-blind NOSE trial and with support from other small studies in Table 6, many of which range from 1.5 to 1.7.

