**Discontinuation Rate:** Table 6 also summarizes early study discontinuation rates for HHT study participants, either due to drop-out (from placebo or treatments with minimal side effects), or due to AEs (from our pilot study of pomalidomide and studies of the more toxic thalidomide). Based on an average of these sources, we anticipate a 10% discontinuation rate during the 24-week treatment interval. Patients with HHT regularly see their doctors and are not expected to be lost to follow-up, and so we anticipate being able to obtain post-baseline ESS scores even for participants who stopped taking the double-blind study drug before that time. We also expect to minimize study discontinuations by allowing patients with some side effects to temporarily halt study drug and then re-start with a lower dose. Nevertheless, it is likely that some participants may discontinue the study without providing any post-baseline data, and it is possible that discontinuations due to AE may be larger than 10%. By planning for 90% power with a 10% discontinuation rate, we plan to have sufficient sample size so that the study would still be well powered if the study discontinuation rate were as high as 30%.

Author	Treatment	N	ESS Baseline mean (SD)	Post-trt assessment time	Rate of Discontinuation, dose-limiting AEs or missing data	ESS Post-BL mean (SD)	ESS Change from baseline Mean (SD), N	Source of SD for change from baseline
[name] pilot study of Epistaxis and GI bleeding	Pomalidomide	9 (8 with epistaxis, 1 with GI bleeding)	5.9 (1.47) N=7 (1 recent enrollment not yet included)	12W	22% (2/9) due to rash at 2W.	3.5 (0.99) N=5	-2.5 (2.11), N=5	Calculated from data
				24W		3.3 (0.61) N=5	-2.7 (1.92), N=5	
Whitehead NOSE study (JAMA 2016) Randomized, double-blind	Bevacizumab, estriol, tranexamic acid, or placebo nasal spray (There were no differences between the 4 TRT groups)	121	5.4 (1.38) N=120	12W	12% (6% patient decision, 6% missing diary data or protocol violation)	3.7 (1.68) N=105	-1.5 (1.48), N=105 By trt grp: B: -1.6 (1.2) E: -1.4 (1.5) TA: -1.4 (1.6) Placebo: -1.7 (1.6)	Calculated from data provided by Author
				12W after TRT stop		4.1 (1.65) N=83	-1.0 (1.53), N=83 SD varied by trt grp: (1.3, 1.3, 1.7, 1.8)	
Dupuis-Girod ELLIPSE study (JAMA 2016) Randomized double-blind	Bevacizumab or placebo nasal spray	80	N/A	6 months	8 % (6% patient decision, 2% missing data or protocol violation)	N/A	N/A	N/A

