10.2 Adverse Events

Per the protocol, participants were asked to report any adverse events from initiation of treatment through 24 weeks follow-up. All adverse events will be collected on an adverse event log and coded using MedDRA.

Adverse events will be listed and summarized by MedDRA system organ class and preferred term. Summaries will be of the number of events and number of individuals experiencing events by treatment group and will be created for all adverse events, by severity, and by relationship to treatment. Any events starting outside of the reportable time frame will be included in separate listings and will be excluded from summary tables. If a complete onset date is unknown and it cannot be confirmed that the event occurred during this time period, then the event will be considered a treatment-emergent adverse event.

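### Toxicity rates per person-month are planned for pomalidomide only, so they have no placebo comparator, and the arms are compared on crude incidence alone

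*SAP*

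**What the plan says.** SAP section 10.1 sets out two safety measures. The first is a between-arm test: "Treatment groups will be compared for incidence of events with a chi-squared or" Fisher's exact test. The second is a person-time rate for one arm: "incidence density (events per person-months of exposure) will be calculated for toxicities in the pomalidomide group". Protocol section 10.4.4 has the same sentence, so the restriction is a stated rule and not a detail left open.

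No other section supplies the placebo rate:

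- SAP section 7.4, for the DSMB: "Rates of safety outcomes will be compared between treatment groups using" Fisher's exact tests, which work on proportions.
- SAP section 10.2, for the adverse event tables: "Summaries will be of the number of events and number of individuals experiencing events by treatment group". No person-time denominator is given.
- SAP section 9.2 speaks of an incidence rate for the listed toxicities but defines no denominator in time.
- SAP section 10.4 compares treatment-emergent laboratory abnormalities as proportions.

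No rate ratio, rate difference or time-to-event comparison of safety is planned.

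**The concern.** By choosing a person-month measure, the plan accepts that time at risk matters. A rate for one arm is hard to interpret when the event also occurs without the drug. Protocol section 6.1.8.6 says that drug-related fatigue may be difficult to tell apart from fatigue due to HHT or anemia. A pomalidomide fatigue rate therefore needs the placebo rate beside it.

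Shorter exposure is foreseen. Protocol section 10.5 plans for 10% discontinuation, allows that stops for adverse events may exceed this, and considers 30%. In the pomalidomide pilot 2 of 9 patients stopped for rash at two weeks. Sections 6.1.8.3, 6.1.8.9 and 6.1.8.12 list toxicities that end study drug. Protocol section 8.3 closes recording of non-serious events 7 days after the last dose and of serious events 30 days after it, so an early stop also shortens the time in which events are counted.

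At stake is the reading of the adverse event tables. Safety and tolerability is the first secondary objective. If exposure is shorter on pomalidomide, crude percentages can make the drug look somewhat safer than it is, and a one-arm rate cannot show this.

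**Working it through.** The plan states no figure on this point, so there is none to reproduce. The check asks how far crude incidence could mislead.

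**Inputs from the documents**

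- Allocation, Protocol section 10.5: "We will randomize 159 patients, 106 on pomalidomide, 53 on placebo".
- Duration, Protocol section 6.1.9: "The duration of pomalidomide therapy will be 24 weeks". That is 168 days, or T = 168/30.4375 = 5.52 months.
- Discontinuation, Protocol section 10.5: "we anticipate a 10% discontinuation rate during the 24-week treatment interval". The highest scenario there is 30%. Both are study-wide.

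**Assumptions**

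- Arm-specific discontinuation: 30% on pomalidomide, 10% on placebo, treated as drug stops.
- Constant hazard λ, equal in both arms: 0.05 or 0.03 per month.
- Observation ends when drug stops. Stops are either spread evenly over 24 weeks or all at week 6 (42/30.4375 = 1.38 months).

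**Formulas**

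- Risk over full exposure: F = 1 − exp(−λT).
- Mean risk for stoppers, even stops: U = 1 − F/(λT).
- Risk for stoppers at week 6: E = 1 − exp(−1.38λ).
- Crude incidence in an arm with share d stopping: (1 − d)F + dX, where X is U or E.
- False difference: (0.30 − 0.10)(F − X).

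**Results**

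| λ per month | F | X | Pomalidomide | Placebo | False advantage |
|---|---|---|---|---|---|
| 0.05, even stops | 24.1% | 12.6% | 20.7% | 23.0% | 2.3 points |
| 0.05, week 6 | 24.1% | 6.7% | 18.9% | 22.4% | 3.5 points |
| 0.03, even stops | 15.3% | 7.8% | 13.0% | 14.5% | 1.5 points |
| 0.03, week 6 | 15.3% | 4.1% | 11.9% | 14.1% | 2.2 points |

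With equal discontinuation the first factor is zero, and so is the distortion. With 10% on pomalidomide and 30% on placebo the sign reverses. With the pilot's 22% against 10%, the factor is 0.12 and the range at 0.05 is 1.4 to 2.1 points.

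**Exposure.** Mean exposure at 30% and 10% is 4.69 and 5.24 months (even stops), or 4.28 and 5.11 months (week 6). This is about 497 and 278, or 453 and 271, person-months.

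**A real excess.** Take a 10% placebo risk over the full 24 weeks and a true rate ratio of 2.0. The crude risk ratio is 1.90 with full exposure in both arms, 1.71 with even stops and 1.60 with stops at week 6.

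**Recording window.** Adding the same window of e months after the last dose in both arms multiplies the false difference by exp(−λe). At 0.05 per month this is exp(−0.05 × 7/30.4375) = 0.99 for non-serious events and exp(−0.05 × 30/30.4375) = 0.95 for serious events. The range hardly moves.

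**The case against.** The strongest reply is that crude incidence in everyone dosed, over a fixed 24-week course, is a valid safety summary, and that the harm is conditional. This stands. The documents give no discontinuation by arm. SAP section 5 mentions participants who stopped drug for adverse events, but not their arm, and two of them stayed under assessment for months afterwards.

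The effect is also small against sampling error. Near 21% incidence, the 95% half-width for a difference is 1.96 × √(0.21 × 0.79 × (1/106 + 1/53)) = 13 points. Under SAP section 7.7, adverse events, as an other secondary outcome, are not judged for statistical significance, so no formal conclusion depends on this.

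Constant hazard does not suit every toxicity. Protocol section 6.1.8.7 says that rash usually appears at drug initiation. For such events crude incidence is little affected by later stopping, while person-time would mislead. If crude incidence were identical and all events came early, the rate ratio would still be 5.24/4.69 = 1.12 or 5.11/4.28 = 1.19. A rate should therefore sit beside the crude test and not replace it. A rate ratio also cannot be estimated for every listed toxicity: blinded review, in SAP section 9.2, found no arterial thromboembolism.

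A reader might infer that the plan lacks a between-arm safety comparison, or that incidence density was meant to correct for unequal follow-up. Neither is supported. A comparison exists, on incidence, and neither document gives the rate that purpose.

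What the objection does not answer is the one-arm rule. A pomalidomide rate with no placebo rate has no comparator, whatever the discontinuation turns out to be.

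**Conclusion.** The gap is real and minor to moderate. Both documents restrict incidence density to pomalidomide, and nothing elsewhere provides an exposure-adjusted comparison. Unequal exposure could bias the crude comparison by about 1.5 to 3.5 points under the stated assumptions. The plausible range includes zero, and the direction depends on which arm stops more.

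A reader might infer a false advantage of 4 points or more, for instance by assuming mean exposure of 4.3 against 5.3 months at 0.05 per month (19.3% against 23.3%). The documents do not support that size. With even stops, a mean of 4.3 months needs 2 × (1 − 4.3/5.52) = 44% discontinuation on pomalidomide, above the highest study-wide scenario of 30%. Nor do they support a statement that the crude comparison is biased in favor of the drug, only that it could be.

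**What to change.** In SAP section 10.1, and in Protocol section 10.4.4 if it is amended, extend incidence density for toxicities to both treatment groups. Report the rate difference, or the rate ratio where both arms have events, with 95% CI. Label this a descriptive supplement. The chi-squared or Fisher's exact test on crude incidence stays.

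Define person-months once, before unmasking: from first dose to last dose plus the adverse event recording window, with rules for dose holds and for first versus recurrent events. The window must be reconciled first. Protocol section 8.3 runs from consent to 7 or 30 days after the last dose, while SAP section 10.2 describes reporting from treatment initiation through 24 weeks.

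Add a note that rate ratios for early-onset events such as rash need care, because shortened person-time inflates the pomalidomide rate.

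The cost is wording and some programming. SAP section 8.3 already uses pill counts and the time from first dose to completion or stop in both arms, and SAP section 14 lets displays be added that do not contradict the text.
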